3.4 Potential Risks to Subject Safety

a) Dapagliflozin.

Likely and not serious:

These risks are expected to occur in more than 20 out of 100 subjects: None

Less likely and not serious:

These risks are expected to occur in 5-20 subjects or less out of 100 subjects: Genital mycotic infections (about 4%) Nasopharingytis and UTI (about 1%) and in less than 4 out of 100 individuals low blood sugar (also called Hypoglycemia)

Rare and serious: loss of consciousness (or syncope), decrease in blood pressure, and dehydration (less than 1%)

Version: 2.4 10-29-2020

b) Blood Withdrawal. All studies involve the withdrawal of blood. Any subject who has donated blood in the previous two months will not be studied. The subjects will be instructed not to donate blood for two months after the study. Any subject with a hematocrit of less than 34% will not be studied. The maximal amount of blood to be drawn during the entire study for any given subject will be approximately 200 mL. Hematology comprehensive metabolic panel with lipids and liver function tests will be obtained to assess effects on blood cell count, liver function and lipid metabolism. Pain, bleeding, bruising or swelling may occur at the site of the needlestick. Study participants may also experience light headedness or fatigue. Local hematomas occur in 1-5% of blood draws. Infection and nerve damage are possible (<1%). A qualified phlebotomist will perform venipunctures to minimize these risks.

- c) IV lines. Intravenous catheters may be used for venipuncture. Local hematomas occur in about 1% of catheterizations. Infection is possible (<1%), but we have not experienced this complication.
- d) Muscle biopsy. At the time of biopsy, subjects may feel pain, discomfort, or pressure (variably described by different subjects) for about 5-10 seconds. Pain or discomfort ceases as soon as the cannula is withdrawn. Some localized bruising is expected after biopsy. Local hematomas occur in <2% of subjects. One patient experienced a moderately painful hematoma that resolved within 2 weeks (0.1%). About 1 in 50 subjects report non-clinically evident numbness or altered sensation at the biopsy site, which is transient. There is the possibility that a future biopsy may not be done at the discretion of the PI in case the subject did not tolerate well a prior biopsy.
- e) Adipose tissue biopsy. A burning discomfort will be felt for about 5-10 seconds during the application of lidocaine. Subjects are likely to bruise at the biopsy site, which generally resolves within one week of the biopsy. Mild wound infections occur in <2% subjects.
- f) Radiation exposure. Subjects will also be exposed to a very small amount of radiation during the DEXA exam (0.04 mrem), which equals one day of natural background radiation.
- q) Home visits. When necessary to perform home visits, study staff will use precautions to reduce the risk of improper disclosure or loss of research records and research specimens. The study staff will not remove any original records from the research site and will only use the minimal amount of PHI necessary to accomplish the home visit. All study records being transported will be secured in a locked file case. Research specimens will be labeled and packed in accordance with the site's laboratory regulations and returned to the research site (FORU) in a carrier regulated for biohazardous materials. Study records and specimens will never be left unattended during the home visit or when being transported to and from the study site.

4. Subject Selection and Withdrawal

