1.4. Dose Rationale and Risk/Benefits

In the DPP trial, weight loss was proportional to diabetes prevention. There are no serious risks to losing weight at a reasonable rate. Dapagliflozin 10mg daily is the maximum daily dose and has been shown to increase glucose urinary excretion more than 5mg daily. Dapagliflozin 10mg/day has been assessed in combination with exenatide treatment in prediabetic patients for one year and shows similar safety and tolerability to previous trials in diabetic patients (35). Dapagliflozin 10mg/day is also in use for the DAPA-HF study in a study population that includes prediabetics (36). Another SGLT2i, empagliflozin, has been assessed in prediabetics at a comparably high dose (25mg/day) for two weeks and did not show AE among treated subjects (37). The SAE's associated with dapagliflozin include acute kidney injury, fall from orthostasis, gangrene of the perineum, and diabetic ketoacidosis. These risks will be mitigated in this study by monitoring subject status with biweekly phone check-ins with patients as well as monthly in-person visits during drug refill visits.

2. Study Objective

The primary objective is to determine whether SGLT2 inhibitors improve biomarkers of aging in older obese adults with pre-diabetes.

The secondary objective is to determine whether changes in aging-related biomarkers resulting from SGLT2i therapy are linked to changes in glucose metabolism and healthspan.

3. Study Design

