6.1.2. Visit 2 (Day --7 to -17 [+/- 2 weeks])+

Eligible subjects will present to the MARC research unit for vital signs, walk distance, grip strength, isometric knee extension strength testing, a body composition DXA scan and liver fibroscan.

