6.1.4. Visit 4 (Day -1 to -6) -- "Optional"

Participants who opt in will come to the research unit for vital signs and VO2max testing.

Cardiorespiratory fitness is determined by a CPET on an electronically braked cycle ergometer per the American College of Sports Medicine (ACSM) Testing Guidelines. Oxygen consumption and carbon dioxide production are measured by indirect calorimetry. ECG (12-lead) recordings and blood pressure are monitored at rest prior to testing and during the testing. A clinician interprets for contraindications to exercise prior to testing. AHA criteria are used to halt exercise testing [43].

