6.1.5. Visit 5 (Day 0)

Eligible subjects present to the research unit fasting at appointed time for a vastus lateralis muscle biopsy (39) and subcutaneous fat biopsy (40). We apply local lidocaine for muscle and adipose biopsies. The muscle biopsy is done using a modified Bergstrom technique with suction and the adipose biopsy is done using a mini-liposuction technique. Urine and blood samples also will be collected. These samples will be used for baseline assays of tissue cellular senescence, DNA methylation, oxidative stress and mitochondrial function. After the muscle and adipose tissue biopsies, subjects will be given breakfast and will receive assignment to treatment intervention (randomized) before being discharged to home. Both treatment and control groups will be given a brochure highlighting healthier eating habits. Subjects in the treatment group will be given a 30-day supply of dapagliflozin to begin use the next day. Subjects in the control group will receive a nutritional consultation with a dietician, which may also be conducted by video telehealth visit, with the goal of losing 3-5% body weight during the 3-month period of the study.

- Once intervention phase begins, the study staff will contact subjects assigned to study drug for telephone follow up at Visit 5 +1 week and at or near midpoint between visits to the research unit up to Visit 8.
- Subjects assigned to nutritional counseling group will receive weekly phone calls/video telehealth visits during the intervention phase which will last for 12 weeks.
- Study team members may contact the subjects by phone at any time for AE follow up as needed.

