6.1.6. Visit 6 (Week 4)

Subjects will come to the research unit for evaluation of the biopsy sites and undergo blood draw for CMP to monitor kidney function. Subjects will also have current weight checked at this visit. If necessary, the study coordinator may conduct Visit 6 by home visit and perform the biopsy site check by video telehealth visit. Control group subjects will receive nutritional counseling, which may be performed by home visit or a video telehealth visit.

Drug Refill: Subjects in the treatment group will be given a 30-day supply of dapagliflozin by the Research Drug Manager to begin when their current supply runs out. Study coordinators will ensure treatment compliance by asking subjects to bring drug containers and any remaining dapagliflozin tablets to their visits.

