8.2. Recording of Adverse Events

At each contact with the subject, the investigator or study staff will seek information about adverse events by specific questioning and, if appropriate, by examination. Information on all AEs will be recorded immediately in the source document, and also in the appropriate AE section of the case report form (CRF). AEs will be tracked using the HSC IRB AE tracking form or data management tool (See Section 9.3) to be reviewed by Site Investigator on a monthly and ad hoc basis, depending on severity and expected/unexpected nature of the event. All subjects will have study compliance calls every two weeks during which AEs can also be reported.

All AEs occurring during the study period will be recorded. The clinical course of each event will be followed until resolution, stabilization, or until it has been determined that the study treatment or participation is not the cause. SAEs that are still ongoing at the end of the study period will be followed up to determine the final outcome. Any SAE that occurs after the study period and is considered to be possibly related to the study treatment or study participation will be recorded and reported per Institutional policy and according to FDA requirements.

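### On dapagliflozin, vital signs are scheduled only at the optional exercise-test visit (Visit 10), so a subject who declines that test has no scheduled blood pressure in 12 weeks of treatment

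*Combined protocol and SAP*

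**What the plan says.** On risk, section 3.4 gives "Rare and serious: loss of consciousness (or syncope), decrease in blood pressure, and dehydration (less than 1"%) under dapagliflozin. Section 1.4 says: "The SAE's associated with dapagliflozin include acute kidney injury, fall from orthostasis, gangrene of the perineum, and diabetic ketoacidosis". It states that these risks will be mitigated by "monitoring subject status with biweekly phone check-ins with patients as well as monthly in-person visits during drug refill visits".

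On detection, section 8.2 says that at each contact the investigator or staff "will seek information about adverse events by specific questioning and, if appropriate, by examination".

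On measurement, section 6.1 names vital signs at four visits. Visit 1 is screening. At Visit 2, "Eligible subjects will present to the MARC research unit for vital signs, walk distance, grip strength, isometric knee extension strength testing". At Visit 4, "Participants who opt in will come to the research unit for vital signs and VO2max testing". Visit 10 repeats Visit 4 at week 11-12 and is also headed optional. The Vital Signs row in section 6.2 is marked at Visits 1, 4 and 10 only, and a footnote to that table confirms that the exercise test is optional.

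Treatment begins after Visit 5: "Subjects in the treatment group will be given a 30-day supply of dapagliflozin to begin use the next day". The week-4 visit has a biopsy-site check, a metabolic panel to follow kidney function, and a weight: "Subjects will also have current weight checked at this visit". It lists no blood pressure.

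**The concern.** The protocol names a fall in blood pressure and its consequences (syncope, falls on standing) as serious drug risks, but it does not require anyone to measure blood pressure during treatment unless the subject volunteers for an exercise test.

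The population makes this relevant. Subjects are 60 or older, and the Study Summary allows standard antihypertensive drugs. The blood-pressure exclusion in section 4.2 sets only upper limits (systolic above 180, diastolic above 100), with no lower one. Section 1.1 itself attributes mild volume depletion and reduced blood pressure to the class, so some fall is an expected drug effect.

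If the schedule is followed as written, a fall in pressure that causes no complaint, or that shows only on standing, goes unrecorded in anyone who declines the test. Staff could then act only once the subject reports symptoms or has fallen. Subjects who take the test have their first scheduled on-drug reading when treatment is almost over.

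**Working it through.** The plan gives no figure to reproduce. The check compares what each visit lists in section 6.1 with the Vital Signs row in section 6.2. Drug starts the day after Visit 5 (Day 0), so the on-drug visits are 6 to 11. Visit 12 (week 13) is post-treatment.

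| Visit | Timing | Main content (6.1) | Vital signs in 6.1 text | Vital signs in 6.2 table |
|---|---|---|---|---|
| 1 | day -17 to -21 | screening | yes | yes |
| 2 | day -7 to -17 | performance tests, DXA | yes | no |
| 4 (optional) | day -1 to -6 | exercise test | yes | yes |
| 5 | Day 0 | biopsies, assignment | no | no |
| 6 | week 4 | biopsy check, metabolic panel, weight | no | no |
| 7 | week 8 | refill (may be by mail or curbside) | no | no |
| 8 | week 10-11 | performance tests, DXA | no | no |
| 9 | week 10-11 | liver MRI | no | no |
| 10 (optional) | week 11-12 | exercise test | yes | yes |
| 11 | week 11-12 | biopsies, metabolic panel | no | no |

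Text and table agree at every on-drug visit, so the result does not come from a badly extracted table. Their one mismatch, Visit 2, is before treatment.

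**Counts.** On-drug visits with scheduled vital signs: 1 of 6. Without optional Visit 10: 0 of 5. Of those five, Visit 7 need not be in person and Visit 9 is an imaging appointment. The firm clinical opportunities are therefore Visits 6, 8 and 11, and none of them has a reading.

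**Time without a reading.** Treatment lasts 12 × 7 = 84 days. A subject who declines the test has 0 scheduled readings in that time. A subject who accepts has the first at week 11-12, which is day 11 × 7 = 77 to day 12 × 7 = 84.

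**Age of the last scheduled reading at day 84, test declined.**
- From the Visit 2 text: 84 + 7 = 91 to 84 + 17 = 101 days, before applying that visit's window of plus or minus 2 weeks.
- From the table, which leaves only Visit 1: 84 + 17 = 101 to 84 + 21 = 105 days.

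**In-person gap if the week-8 refill is remote.** From Visit 6 at week 4 to Visit 8 or 9 at week 10-11: 10 - 4 = 6 to 11 - 4 = 7 weeks. The window on Visits 8 and 9 could move them later, but Visit 11, which is not optional and has no stated window, falls by week 12. The maximum is 12 - 4 = 8 weeks.

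**Expected events.** Section 3.1 plans 20 completers split evenly, so 10 on dapagliflozin. At a rate below 1%, each listed risk gives fewer than 0.01 × 10 = 0.1 expected events.

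**The case against.** The strongest reply is that on-drug safety is monitored and that little harm is likely. Section 6.2 has adverse events assessed at every visit from 2 to 12 and schedules calls to the drug arm. Section 8.2 requires questioning at each contact and allows examination. The metabolic panel at Visit 6, repeated at Visit 11, is a mandatory objective check relevant to volume depletion and acute kidney injury. Section 10.1 requires prompt review of adverse events by the principal investigator. Section 4.2 excludes subjects with eGFR below 45, a recent cardiovascular event or advanced heart failure. This is a 12-week pilot of a marketed drug with 20 completers, and blood pressure is not an endpoint.

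All of that stands, and it limits how much weight the point can bear. It does not close the gap. Questioning and phone calls find symptoms, a metabolic panel does not measure pressure, and examination under section 8.2 is discretionary. Staff may well take vital signs at biopsy visits by habit, but the protocol does not ask for it.

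A reader might infer three stronger things that the documents do not support:
- **That the schedule contradicts section 1.4.** That section promises monitoring of subject status by phone and at refill visits. It does not promise blood-pressure readings.
- **That the protocol rates any fall in pressure as serious.** Section 3.4 groups the decrease with syncope and dehydration, which reads naturally as a clinically significant event. The Study Summary counts improved blood pressure among the drug's benefits. An asymptomatic fall has no action threshold anywhere.
- **That no treated subject has blood pressure taken.** Those who take the exercise test do, at rest and during the test. The documents give no uptake figure, so the number affected is unknown: anywhere from 0 to 10 of the 10 drug-arm completers.

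**Conclusion.** The point holds as a gap in scheduled monitoring. Readings on drug depend entirely on opting in to the exercise test, and even then come only at week 11-12. For a subject who opts out, the plan schedules no blood pressure in 84 days of treatment, against risks that it names itself.

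The likely consequence is small in numbers, and the primary endpoint and its analysis are not affected. What is lost is the chance to see a falling or orthostatic pressure before it causes symptoms. That makes it a cheap improvement worth making, not a reason to stop or redesign the trial.

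The conclusion assumes that the schedule is followed as written, that the rate in section 3.4 applies to each listed risk in this population, and that Visit 11 takes place by week 12.

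**What to change.** Add sitting and standing blood pressure and pulse at:
- Visit 5, before the first dose, to give a baseline at the start of treatment;
- Visit 6, including when it is done as a home visit, with staff taking the reading there;
- Visit 11;
- Visit 7, when the subject attends in person.

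Do this at least in the dapagliflozin arm, and mark the visits in the Vital Signs row of section 6.2. A subject who declines the exercise test would then have two scheduled on-drug readings (week 4 and week 11-12), or three with an in-person week 8, instead of none.

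In the same amendment it would be tidy to mark Visit 2 in that row to match its text, and to say in section 1.4 that the week-8 refill may be remote.

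The cost is a few minutes at each existing visit and one amendment, with no added visit, blood draw or invasive procedure.

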Inclusion Criteria	Men and post-menopausal women age 60 and above; BMI 30-38 (BMI 29.5 will be rounded up); diagnosis of pre-diabetes (HbA1c 5.7-6.4%); stable body weight (±3% for ≥3 months); Montreal Cognitive Assessment 21 and above; Subjects must be in good general health as determined by physical exam, medical history, blood chemistries, CBC, TSH, lipid profile, EKG and urinalysis.
Exclusion Criteria	Diagnosis of diabetes based on ADA criteria; impaired renal function with eGFR < 45 mL/min/1.73m²; impaired liver function with labs 3x ULN and above; hematocrit with LLN 30% and below; triglycerides with ULN 600 mg/dL and above; abnormal TSH of 0.3 and below to 10 and above; urinalysis with >5-10 WBC; history of frequent UTI; poorly controlled blood pressure (sysBP >180, diaBP > 100 mmHg); history of recent cardiovascular event in prior 6 months, heart failure, active heart disease; current treatment with drugs known to affect glucose and lipid homeostasis; current treatment with anticoagulants (aspirin <326 mg and clopidogrel permitted if held 7 days prior to biopsies; active inflammatory, autoimmune, gastrointestinal, hepatic, infectious, malignant or uncontrolled psychiatric disease (controlled depression, anxiety, PTSD, etc. enrollment allowed); ; blood donation within 2 months prior to enrollment.
Concomitant Medications	Allowed: Standard of care medications for the management of hypertension, hyperlipidemia and other drugs that at the discretion of the investigator will not interfere with the results of the study. If patient on drugs that affect metabolism like levothyroxine, should be on a stable dose for the last 3 months. Prohibited: Any medications known to adversely affect glucose and lipid metabolism. Additionally, patients on warfarin or other blood thinners except for aspirin up to 325mg and clopidogrel will be excluded.

Study Product, Dose, Route, Regimen	Dapagliflozin, 10mg, Oral, Daily
Duration of administration	12 weeks

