3.2. General Design

This is a single center, open-label, randomized controlled trial. 20 completed subjects are planned. Each subject will be randomized to either the experimental group of dapagliflozin 10mg daily for 12 weeks or the control group of nutritional counseling for weight loss. Healthspan and clinical evaluations will be taken at baseline and at weeks 10-12 of the study.

Screening data will be reviewed to determine subject eligibility. Subjects who meet all inclusion criteria and none of the exclusion criteria will be entered into the study.

The following treatment regimens will be used:

- Dapagliflozin: 10mg per day for 12 weeks. Subjects will return to refill drug medication and perform compliance check at 4 weeks and 8 weeks after beginning treatment.
- Control Group: Subjects will meet with a dietitian every 1-2 weeks throughout the study to discuss nutritional counseling with a goal to lose 3-5% of body weight over 12 weeks to mirror expected SGLT2

inhibitor-derived weight loss over the same period. During these hour-long sessions, volunteers will learn how to adjust their eating habits by following the recommendations of the American Heart Association for reducing dietary fat and substituting complex carbohydrates and reducing energy intake to induce gradual weight loss while maintaining recommended dietary composition. Volunteers also will receive education on portion sizes, meal timing, and meal preparation. Participants receive a notebook of course content and will weigh in prior to each session. Additional counseling visits and/or phone calls may be instituted if desirable weight loss is not achieved. Subjects may be asked to record their dietary intake for a 24-hour period throughout the intervention for review by the dietitian.

Total duration of subject treatment will be 12 weeks. Total duration of the study is expected to be 16-18 weeks.

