4.2. Exclusion Criteria

- 1) Diagnosis of diabetes based on ADA criteria
- 2) Impaired renal function with eGFR < 45 mL/min/1.73m². Unstable or rapidly progressing renal failure.
- 3) Impaired liver function with labs ≥3 times upper limits of normal range
- 4) Abnormal hematocrit with lower limits of ≤30%
- 5) Abnormal triglycerides with upper limits ≥600 mg/dL
- 6) Abnormal TSH values ≤0.3 and ≥10
- 7) Urinalysis results with >5-10 white blood cell count
- 8) Current medications known to affect glucose and lipid homeostasis (anti-diabetes medications, glucocorticoids, atypical antipsychotics, anti-transplant rejection medications, anti-retrovirals).
- 9) Current treatment with anticoagulants (warfarin). Aspirin (up to 325 mg) and clopidogrel will be permitted if these can be held for seven days prior to the biopsies.
- 10) History of recent cardiovascular event in the last 6 months or Heart Failure (New York Heart Classification greater than class III-IV; recent EKG changes that suggest active heart disease
- 11) Poorly controlled blood pressure (systolic BP>180, diastolic BP>100 mmHg)
- 12) Active inflammatory, autoimmune, infectious, hepatic, gastrointestinal, malignant, and uncontrolled psychiatric disease (Subjects with depression, anxiety, PTSD, etc. can enroll if controlled and on stable medication)
- 13) Blood donation within 2 months prior to enrollment
- 14) History of frequent UTI

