6.1.1. Visit 1 (Day -17 to -21)

Eligible subjects present to the research unit at appointed time for informed consent. Consenting subjects will arrive fasting to undergo vital sign evaluation, medical history, physical exam, safety labs [comprehensive metabolic panel (CMP), complete blood count with differential (CBC), coagulation labs (PT/PTT/INR), HbA1c, TSH, routine urinalysis, lipid panel, insulin and FFA, and the Montreal Cognitive Assessment (participants must score ≥21 to be eligible). Visit results will help determine eligibility for study inclusion (i.e. HbA1c 5.7-6.4%).

Investigators will routinely assess laboratory value excursions for clinical significance.

Adverse events are assessed at every visit once subjects are consented and enrolled to undergo research procedures and study intervention.

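### The protocol gives two haematocrit limits for entry (below 34% and 30% or below) and two different heart failure exclusions

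*Combined protocol and SAP*

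**What the plan says.** **Haematocrit.** Three places in the protocol state a limit.

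- Section 3.4(b), Blood Withdrawal: "Any subject with a hematocrit of less than 34% will not be studied".
- Section 4.2, item 4: "Abnormal hematocrit with lower limits of ≤30" (percent).
- Study Summary, Exclusion Criteria: "hematocrit with LLN 30% and below".

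The entry rule is in section 3.2: "Subjects who meet all inclusion criteria and none of the exclusion criteria will be entered into the study". The result it acts on comes from Visit 1, where section 6.1.1 lists "complete blood count with differential (CBC), coagulation labs (PT/PTT/INR" among the safety labs.

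**Heart failure.** The Study Summary lists heart failure as an exclusion with no severity qualifier. Section 4.2 item 10 qualifies it: the New York Heart class has to be greater than the range III-IV. The parenthesis that opens there is never closed.

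**EKG.** The Study Summary names an EKG among the tests that establish good general health, and item 10 refers to recent EKG changes. Sections 6.1.1 and 6.1.2 (Visits 1 and 2, the screening visits) list no EKG, and the schedule in section 6.2 has no row for one. The only ECG described belongs to the optional exercise test in section 6.1.4.

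**The concern.** An eligibility limit should give one answer for one candidate. Here a coordinator working from section 4.2 would enrol someone whom section 3.4(b) says is not to be studied, on the same blood count. A candidate with milder heart failure is excluded by the Study Summary but not by the heart failure clause of item 10.

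Both rules protect participants. The study enrols adults aged 60 and above, draws up to about 200 mL of blood and takes muscle and fat biopsies twice. Section 8.4.1 also requires departures from the protocol to be reported to the IRB. With two limits in force, staff cannot tell whether enrolling a candidate at 32% complies with the protocol or is a reportable departure.

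**Working it through.** The check compares current text with current text. It does not rely on the summary of changes, and no sample-size or power figure enters.

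**1. Haematocrit: where the rules agree and disagree.** Let x be the screening haematocrit in percent. Section 4.2 item 4 and the Study Summary exclude x ≤ 30. Section 3.4(b) bars x < 34.

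| Result | 4.2 item 4 and Study Summary | 3.4(b) |
|---|---|---|
| x ≤ 30 | excluded | barred |
| 30 < x < 34 | not excluded | barred |
| x ≥ 34 | not excluded | not barred |

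The rules disagree only for 30 < x < 34. Exactly 30% is excluded by both and exactly 34% by neither. In whole numbers the conflict covers 31, 32 and 33, which is 3 values. If results are reported to one decimal, it runs from 30.1 to 33.9: (33.9 − 30.1)/0.1 + 1 = 39 values. The protocol does not state the reporting precision, so both counts are illustrations; neither says how many candidates fall there.

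**2. Is 3.4(b) an entry rule?** The paragraph makes two statements about who will not be studied. The first concerns blood donation: "Any subject who has donated blood in the previous two months will not be studied". It matches section 4.2 item 13 ("Blood donation within 2 months prior to enrollment") and the Study Summary ("blood donation within 2 months prior to enrollment"). The second is the haematocrit sentence, which matches neither place. So the paragraph does state entry rules, and one of the two disagrees with the lists.

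**3. Could 3.4(b) be a rule for later blood draws instead?** Section 6.2 schedules a CBC only at Visits 1 and 11. A candidate at 31% to 33% at Visit 1 would still be admitted by one rule and barred by the other.

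**4. Heart failure.** A greater-than condition applied to a two-class range can be read in three ways: class III and above, above class III, or above class IV. Each leaves at least classes I and II outside the heart failure clause of item 10, while the Study Summary excludes them. The two texts therefore differ whichever reading is intended.

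**5. EKG.** Of the two screening visits, 0 list an EKG. Section 9.3 leaves the identification of source data to a separate list of forms, and section 9.3.1 accepts medical-record data as source. An existing tracing may be what is meant, but the protocol does not say so.

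**The case against.** The strongest reply on haematocrit is that section 4.2 plainly governs. Section 3.2 ties entry to the inclusion and exclusion criteria, these are listed under those headings in 4.1 and 4.2, the Study Summary agrees with 4.2, and the 34% figure stands once, in a description of risks. The two rules can also be applied together by not studying anyone who fails either. This lowers the practical ambiguity but does not remove it. The sentence in 3.4(b) is categorical, its companion on blood donation is a genuine entry criterion, and no clause tells staff to ignore it or to apply the stricter of the two.

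On heart failure, a summary may abbreviate, and the same entry shortens other items. It also requires good general health, which leaves room for clinical judgement. But dropping a severity limit changes who is excluded. The good-health requirement does not appear in section 4.1 and sets no class. Even if 4.2 alone governs, item 10 cannot be applied uniformly as written. It is fair to say that this part is less firm than two conflicting numbers.

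The objection on the EKG largely stands. No passage contradicts another; a detail is missing. It is kept only as a secondary clarification.

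**Conclusion.** The concern holds. The current text sets two haematocrit limits that disagree for every result above 30% and below 34%, and nothing in the protocol reconciles them. It also sets two heart failure exclusions, one without a class limit and one with a limit that is unclear and narrower on all three readings.

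The conflict acts on screened candidates, up to 100 under section 4.3. The protocol gives no haematocrit distribution and no heart failure prevalence, so the number affected is unknown and may be small. No endpoint or analysis method changes. The point should be fixed because these are safety limits that decide who enters. The conclusion rests on the wording alone; the only assumption is the reporting precision behind the counts of 3 and 39 values.

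**What to change.** - Reconcile section 3.4(b), section 4.2 item 4 and the Study Summary so that they state one haematocrit limit.
- Reconcile section 4.2 item 10 with the Study Summary on heart failure, in words that set a single boundary, and close the open parenthesis.
- As a secondary clarification, add one sentence naming the record used for the EKG element of eligibility.

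Which limit and which class rule apply is for the investigators to decide; no view is taken here. The cost is a wording amendment to the Study Summary, section 3.4(b) and section 4.2 items 4 and 10, plus the one EKG sentence.
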